Therefore, this study will aim to perform a head to head comparison of typhoid tests currently available in the market in two different and geographically distant countries and simultaneously develop a sample set that can be used in future evaluations of emerging technologies and/or to support innovative test development. The knowledge gained from this trial may benefit society by providing information on diagnostic accuracy of currently available point of care typhoid tests. Further the data obtained in this trial will be made available to WHO to support the EDL and stakeholder decision making more broadly.

TRIAL OBJECTIVES AND ENDPOINTS

General Objective

To compare commercially available typhoid point of care tests (RDTs) against a defined reference standard of blood culture and simultaneously develop a sample set to evaluate emerging technologies and/or to support innovation test development.

Primary Objective

- 1.1. To evaluate different RDTs that are commercially available internationally for detecting antigens or antibodies to *Salmonella* Typhi and use Blood culture as standard for comparison.
- 1.2. Establish a biorepository of well characterized specimen collection that can be used to evaluate emerging tests.

Secondary Objectives

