The reported values for prevalence of Salmonella Typhi positive patients in Kenya is 5% (Data from personal communication with [name] Co-PI). The reported values of sensitivity and specificity of diagnostic tests are generally low, (Review article on typhoid RDTs summarizes TUBEX test from IDL Biotech has sensitivity of 78% and specificity of 87%, TestTM It from LifeAssay has sensitivity of 69% and specificity of 90%, Typhidot from Reszon Diagnostic has sensitivity of 78% and specificity of 77%.(9) Similarly reported sensitivity and specificity of SD Bioline Salmonella Typhi IgG/IgM from Abbot and Typhoid IgG/IgM Combo rapid test from CTK Biotech are 69%/76% and 40-79%/68-79% respectively (15)). For the purpose of determining the sample size, sensitivity and specificity were both assumed to be 50%, which corresponds to the scenario that requires the highest number of samples to estimate sensitivity and specificity. Based on this hypothesis, and on the feasibility of recruitment at the sites of enrolment, it was decided to set the sample size in order to recruit at least 100 culture positive and culture negative samples in Kenya. These sample sizes will allow to estimate the sensitivity of the test with 80% power to detect a 95% confidence interval of width of +/- 14% in Kenya (11). Based on the prevalence mentioned above, this number of positive samples requires the enrolment of at least 2,000 participants in Kenya (at a prevalence of 5%). From a similar study carried out by an MSc student in our lab that we supervised (Performance of tubex® tf IGM antibody test against culture in typhoid fever detection in Nairobi county, MSc Thesis by [name], JKUAT, 2019), the average number of patients presenting with febrile illnesses at Mbagathi County Hospital was 20 per day, using this as a basis and considering their relatively smaller sizes, we estimate that for Medical Missionaries of Mary, Reuben Centre Hospital and City Council Clinic, we will have 10 and 5 patients presenting per day in Medical Missionaries of Mary, Reuben Centre Hospital and City Council Clinic respectively. We plan to sample for only 3 days in a week (Mon-Wed) due to the observed trend of high patient inflow on these days from [name]

[name]'s MSc work (total 35 patients per day, 420 per month). This works out to a minimum of 2,520 which is above the sample size of 2,000 participants that we are targeting.

TRIAL PROCEDURES

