The statistical analysis plan (SAP) will be developed and finalized before the start of enrolment and will describe in detail the methodology used to evaluate each of the endpoints. This section is a summary of the planned statistical analyses of the primary and secondary endpoints.

Endpoint	Statistical Analysis Methods
1.1	Point estimates of sensitivity and specificity for each test with 95% confidence interval, using Blood culture as reference standard.
1.2	Establish a biorepository of well characterized specimen collection that can be used to evaluate emerging tests.
2.2	Evaluation of operational characteristics of different RDTs including invalid and indeterminate rates.

- Efficacy Analyses

Analysis datasets

The following datasets will be defined:

- ITT (Intention-To-Test) all subjects successfully enrolled in the study
- MITT (Modified-Intention-To-Test) all subjects in ITT for whom at least one test result is available
- PP (Per-Protocol) all subjects in ITT for whom results for all tests are available (complying with the protocol)

Description of statistical methods

General approach

Estimates of accuracy

Table 5 summarizes the way results of diagnostic tests are reported when two tests are compared. Based on the definitions in the table, the following values are defined:

Sensitivity = TP / (TP + FN)

Specificity = TN / (FP + TN)

For each point estimate, a 95% confidence interval will be derived based on the Wilson's score method. Missing and invalid results (e.g. the results for one specific test for a given participant) will not be imputed and will be removed from the analysis.

Table 5 Definition of test results

	Reference Standard Outcome								
t		Reference positive	Reference negative	Total					
result	Test result Positive	ТР	FP	PP = TP + FP					
Test	Test result negative	FN	TN	PN = FN + TN					
	Total	P = TP + FN	N = FP + TN	P + N					

TP = true positives, TN = true negatives, FP = false positives, FN = false negatives, P = positive, N = negative

Analysis of the primary outcome(s)

Outcome 1.1

This outcome will be evaluated with the methodology described in section 4.1.1, using using blood culture as reference standard, on the PP population, for each test included in the trial. Outcome 1.2

This outcome does not require any statistical analysis.

Analysis of the secondary outcome(s)

Outcome 2.1

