	Initial Test Result (IgG)	//	Pos	
			🖵 Neg	
			□Inv	
	Repeat testing if invalid	//	□Pos	
SD Bioline	results (IgG)		🖵 Neg	
TYPHI IgG/IgM			□Inv	
Fast	Initial Test Result (IgM)	//	□Pos	
			🖵 Neg	
			□Inv	
	Repeat testing if invalid	//	Pos	
	results (IgM)		🖵 Neg	
SD Bioline SALMONELLA	results Initial Test Result (IgG) Repeat testing if invalid results (IgG) Initial Test Result (IgM) Repeat testing if invalid		InvPosNegInvPosNegNegInvPosInv	

			□Inv
	Initial Test Result (IgG)	//	□Pos □ Neg □Inv
Typhoid IgG/IgM Combo Rapid	Repeat testing if invalid results) IgG	//	□Pos □ Neg □Inv
test CE	Initial Test Result (IgM)	//	□Pos □ Neg □Inv
	Repeat testing if invalid results (IgM)	//	□Pos □ Neg □Inv
Enterocheck WB	Initial Test Result	//	□Pos □ Neg □Inv
	Repeat testing if invalid results	//	□Pos □ Neg □Inv
Test it [™] Typhoid IgM	Initial Test Result	//	□Pos □ Neg □Inv

T				
	Repeat testing if invalid results	//	□Pos	
	results		🖵 Neg	
			□Inv	
	Initial Test Result (IgG)	//	□Pos	
			🖵 Neg	
			□Inv	
	Repeat testing if invalid results) IgG	//	□Pos	
Typhoid IgG/IgM			🖵 Neg	
Rapid Test			□Inv	
Casette	Initial Test Result (IgM)	//	□Pos	
			🖵 Neg	
			□Inv	
	Repeat testing if invalid results (IgM)	//	□Pos	
			🖵 Neg	
			□Inv	
	Initial Test Result	//	□Pos	
			🖵 Neg	
S.Typhi- S.Paratyphi "A"			□Inv	
Direct Antigen Detection	Repeat testing if invalid	//	Pos	
	results		🖵 Neg	
			□Inv	
DiaquickS.Typhi	Initial Test Result (IgG)	//	□Pos	
IgG/IgM Ab			🖵 Neg	

			□Inv		
	Repeat testing if invalid results (IgG)	//	Pos		
			🗅 Neg		
			□Inv		
	Initial Test Result (IgM)	//	□Pos		
			□ Neg		
			□Inv		
	Repeat testing if invalid	//	□Pos		
	results (IgM)		D Neg		
			□Inv		
	Initial Test Result	//	□Pos		
			D Neg		
DiaquickS.typhi/ paratyphi Ag			□Inv		
cassette	Repeat testing if invalid	//	□Pos		
	results		D Neg		
			□Inv		
If any of the RDTs not done, put an explanation in comments below.					

Comments	Date (DD/MM/YY)	Initials	Signature
	//		
	//		

//	

Data entry agent initials: _ _ _

Date of completion of data entry (DD/MM/YYYY): ___/__/____

Investigator's Signature: _____

Date of signature (DD/MM/YYY): ___/__/___

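### Accuracy of each test is estimated only in participants with results on all 11 tests, so one test not done discards valid results on the other ten; the CRF also has no code for indeterminate reads

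*Combined protocol and SAP*

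**What the plan says.** Three statements in the Statistical Analysis Plan section bear on the primary analysis.

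- Under Analysis datasets, the per-protocol (PP) set is "PP (Per-Protocol) all subjects in ITT for whom results for all tests are available (complying with the protocol". A modified set needing at least one result (MITT) is also defined, but no analysis uses it.
- Under Outcome 1.1, sensitivity and specificity are evaluated "on the PP population, for each test included in the trial".
- Under Estimates of accuracy: "Missing and invalid results (e.g. the results for one specific test for a given participant) will not be imputed and will be removed".

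The introduction to the section says "This section is a summary of the planned statistical analyses of the primary and secondary endpoints" and promises a detailed SAP before enrolment starts. Table 2 lists 11 index tests: ten RDTs and Widal. The RDT form in Appendix 1 instructs: "If any of the RDTs not done, put an explanation in comments below".

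Secondary endpoint 2.1 and its analysis call for both invalid and indeterminate results, counted for each RDT. Every line of the RDT form, initial and repeat, offers three boxes only: positive, negative and invalid. A repeat is triggered only by an invalid result.

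**The concern.** Outcome 1.1 is a separate estimate for each test, yet membership of its analysis set depends on all the other tests. A culture-positive participant with ten valid results and one test not done contributes to none of the 11 sensitivities. Culture positives are the scarce resource: the Sample Size section says "this number of positive samples requires the enrolment of at least 2,000 participants in Kenya (at a prevalence of 5"%), or 20 enrolments for each positive, with no allowance for lost results.

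The removal rule for missing and invalid results is illustrated at the level of one test in one participant. Inside a set complete on all tests, no missing result is left to remove. The rules can be applied in sequence, PP first and removal second, so they do not strictly contradict each other, but the plan does not say how they combine. Nor does it say whether an invalid entry counts as an available result for PP. The loss below is therefore confined to tests not done.

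The form raises a second issue. A read that is neither positive, negative nor invalid has no coded field, no row in Table 5, and no mention in the removal rule. The indeterminate rate would have to be rebuilt from comments or notebooks. If a reader forces such a read into one of the three boxes, it enters the accuracy estimates or the invalid count unrecognised.

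**Working it through.** **Inputs from the documents.** 100 culture positives (the planned minimum); sensitivity assumed 50%; "80% power to detect a 95% confidence interval of width of +/- 14% in Kenya"; prevalence 5%; 11 index tests; Wilson 95% intervals.

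**Assumed inputs.** The chance q that a given test is missing for a given participant is set at 1% and 2%. Losses are taken either as independent across tests or as correlated within participant at 0.3.

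**The plan's own figures.** n = (1.96 + 0.84)² × 0.25 / 0.14² ≈ 100, and 100 / 0.05 = 2,000 enrolled. Turned round, power = Φ(0.14√n / 0.5 − 1.96), which is 80.0% at n = 100. The Wilson half-width at n = 100 and 50% is 9.6 points. The sample size reproduces.

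**Share kept.**

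- Test-by-test rule: 1 − q.
- PP, independent losses: (1 − q)¹¹, that is 0.99¹¹ = 0.895 and 0.98¹¹ = 0.801.
- PP, correlated losses: the beta-binomial probability of no loss in 11 tests, with mean q and correlation 0.3, which gives 0.956 and 0.913.

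**Results per 100 culture positives.** Each cell shows q = 1% / 2%.

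| Quantity | Test-by-test | PP, correlated | PP, independent |
|---|---|---|---|
| Positives analysed | 99 / 98 | 95.6 / 91.3 | 89.5 / 80.1 |
| Power for ±14% | 79.6% / 79.2% | 78.2% / 76.3% | 75.5% / 70.7% |
| Wilson half-width at 50% (points) | 9.7 / 9.7 | 9.8 / 10.0 | 10.1 / 10.7 |
| Valid results discarded | 0 / 0 | 38 / 73 | 104 / 197 |
| Enrolment to keep 100 positives | 2,020 / 2,041 | 2,093 / 2,190 | 2,234 / 2,498 |

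Valid results discarded are 1,100 × (1 − q) − 1,100 × (share kept), out of 1,089 / 1,078 valid results. Enrolment is 2,000 / (share kept). If all losses fall in the same participants, the PP share equals 1 − q and the gap is zero.

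**Indeterminate reads.** No arithmetic applies. Endpoint 2.1 and the Outcome 2.1 analysis name two categories; the form records one of them. The invalid rate can be computed from coded data and the indeterminate rate cannot.

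**The case against.** The strongest case for leaving the rule alone has four parts.

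- **Head-to-head aim.** The Justification says "this study will aim to perform a head to head comparison of typhoid tests currently available in the market", and a common complete sample is the natural basis for that. This stands as a reason to keep the complete set, but not to make it the sole basis of 11 separate estimates.
- **Size.** The loss rates are assumed. All tests use the same participant's serum, so a short sample would tend to affect several tests together and narrow the gap. Stored aliquots might fill some gaps, although the plan reserves them for future evaluations. Endpoint 1.1 is an interval estimate, so the power figures describe the sizing calculation and not a planned test. Even in the worst case above, the half-width grows only from 9.6 to 10.7 points, and enrolment needs stay under the 2,520 patients the plan projects. All of this stands, and it limits the finding to lost efficiency. No bias is shown.
- **Deferred detail.** The full SAP may settle how the rules combine, and the test-level wording of the removal rule suggests that a test-by-test analysis may be intended. That is possible, but the section already names PP as the set for Outcome 1.1, so the SAP would have to change it.
- **Indeterminate reads may not occur.** Whether any of these tests can give one depends on package inserts not reproduced in the protocol, and the form has a comments column. That is fair, but the endpoint promises the rate, and a free-text column does not define a category.

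**Conclusion.** Both parts hold. As written, Outcome 1.1 sets aside valid results on culture positives whenever another index test was not done. With an assumed 1% to 2% loss per test, PP analyses about 91 to 96 of 100 positives under within-participant correlation of 0.3, and 80 to 90 under independence, against 98 to 99 test by test. Power on the plan's own criterion is 76% to 78% or 71% to 75%, against 79% to 80%. Every Wilson half-width stays inside ±14 points, and complete clustering of losses removes the difference. This is an inefficient and unreconciled rule, not a threat to the study's validity, and it is worth correcting because the correction is nearly free.

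The missing indeterminate code is a plain mismatch between endpoint 2.1 and the form. It does not affect the invalid rate if invalid results are recorded correctly.

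**What to change.** **Analysis set.** For each test, make the primary set all participants selected for index testing who have a valid culture result and a valid result on that test, using the repeat result when the initial one is invalid. Keep the all-tests-complete set as a sensitivity analysis for comparing tests on a common sample. Report the denominator for each test.

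**Indeterminate reads.** Define the term from each manufacturer's instructions where such a read exists, add that code to the initial and repeat lines of those tests on the RDT form, and state how it enters Table 5.

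**Cost.** One paragraph in the SAP, which is due before enrolment, plus one definition and one tick box on the lines concerned, in place before the first monthly batch is tested. The downside is slightly different denominators across tests, which the common-sample analysis covers.

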Presumed diagnosis by the clinician:	□Enteric fever	Dengue	□Other:

BLOOD COLLECTION
1. Blood sample drawn Image: DYES Image: DNO 2. Blood sample draw date (DD/MM/YYYY): _/ / at (24h00) _ :
3. If not blood drawn, why? □Patient Refused □Supply shortage □Unable/difficult to draw

Comments	Date (DD/MM/YY)	Initials	Signature
	//		
	//		
	//		

Data entry agent initials: _ _ _

Date of completion of data entry (DD/MM/YYYY): ___/__/___

Investigator's Signature: _____

Date of signature (DD/MM/YYYY): ___/___/

CASE REPORT FORM-Blood culture V1.0 Commercial typhoid test validation

REFF	REFERENCE TESTING BY BLOOD CULTURE					
1.	1. Technical operator initials:					
2.	2. Aerobic blood culture performed (If no, put an explanation in comments) \Box Yes \Box No					
3.	Aerobic blood culture	Incubation date (DD/MM/YYYY): //	Positive If Positive: Date (DD/MN Time (24h00):	□ Negative □Contamination //YYYY)://		
4.	4. Salmonella Typhi		□Positive	□ Negative		
5.	5. Other clinically relevant growth					
6.	Contamina	nts growth				
7. Data reported to patients		☐ Yes, Date (1 ///				

Comments	Date (DD/MM/YY)	Initials	Signature
	//		
	///		
	//		

Version 2.0, 12th Dec 2020

Data entry agent initials: _ _ _

Date of completion of data entry (DD/MM/YYYY): ___/__/____

Investigator's Signature: _____

Date of signature (DD/MM/YYYY): ___/___/

CASE REPORT FORM-Serum preparation V1.0 Commercial typhoid test validation

SERUM PREPARATION				
1. Serum prepared	 Yes, if yes, Date (DD/MM/YYYY)://///			
If yes at 1. Serum stored?	 □Yes If yes, aliquots stored Storage Location: □ No, if No Why: 			

Comments	Date (DD/MM/YY)	Initials	Signature
	//		
	/ /		
	//		

Data entry agent initials: _ _ _

Date of completion of data entry: ___/__/___/

Investigator's Signature: _____

Date of signature (DD/MM/YYYY): ___/__/____

CASE REPORT FORM-RDTsV1.0 Commercial typhoid test validation

A. TYPHOID RDTs EVALUATION							
	Test Results						
Test name		Date (DD/MM/YYYY)	Results	Comments			
Widal Test	Initial Test Result	//	□Pos □ Neg □Inv				
	Repeat testing if invalid results	//	□Pos □ Neg □Inv				
Typhidot Rapid IgG/IgM combo test	Initial Test Result (IgG)	//	□Pos □ Neg □Inv				
	Repeat testing if invalid results (IgG)	//	□Pos □ Neg □Inv				

1		1		
	Initial Test Result (IgM)	//	□Pos	
			🖵 Neg	
			□Inv	
	Repeat testing if invalid	//	□Pos	
	results (IgM)		🖵 Neg	
			□Inv	
	Initial Test Result	//	□Pos	
			🖵 Neg	
TUBEX TF			□Inv	
	Repeat testing if invalid	//	□Pos	
	results		🖵 Neg	
			□Inv	

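### Accuracy is planned only among readable index-test results; a supplementary estimate over all sera tested would be a cheap improvement to the comparison of the 11 tests

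*Combined protocol and SAP*

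**What the plan says.** Under Estimates of accuracy in the Statistical Analysis Plan section, missing and invalid results are handled by one rule: they "will not be imputed and will be removed from the analysis". The example given there is one test's result for one participant. Table 5 has rows for positive and negative test results only. Sensitivity and specificity are built from its four cells, so an invalid result has no place in either formula.

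Outcome 1.1 is evaluated "on the PP population, for each test included in the trial". The Analysis datasets list defines that set as enrolled subjects who have results for all tests. The same list has "ITT (Intention-To-Test) all subjects successfully enrolled in the study".

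Outcome 2.1 reports, for each RDT, the number of indeterminate and invalid results and their percentage of all tests performed. The RDT case report form in Appendix 1 has a line "Repeat testing if invalid results" for each test, or for each antibody line where IgG and IgM are read separately. The analysis text does not say which of the two results is used.

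The Justification section says that the study will "perform a head to head comparison of typhoid tests currently available in the market". Table 2 lists 11 index tests, including Widal.

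**The concern.** A test that was not run and a test that was run but gave no readable result are different events. The first usually says nothing about the device. The second, if it persists after a repeat, is a failure of that device on that serum, and in use the patient would have no answer. The plan removes both in the same way, and no planned analysis counts the second.

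Each accuracy figure is then accuracy given that the test worked. For one test taken alone, that is a coherent quantity. In a comparison of 11 tests, the share of sera that each can read may differ. A reader who sets the figures side by side, including those who advise on the WHO Essential Diagnostics List, may prefer a test that gives correct answers on fewer of the sera put to it. The Wilson interval does not show this, because it describes sampling error around the conditional figure.

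**Working it through.** **Inputs.** From Sample Size: at least 100 culture-positive and 100 culture-negative samples; quoted literature values of 78% sensitivity and 87% specificity for one test, and 69% and 90% for another. From Table 2: 11 tests. The documents give no invalid rate, so v, the share of results still invalid after the repeat, is assumed. The quoted accuracies serve only as illustration and are taken as accuracy on readable sera.

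**The plan's own figure.** n = (1.960 + 0.842)² × 0.5 × 0.5 / 0.14² = 7.849 × 0.25 / 0.0196 = 100.1, which agrees with the stated 100. At 5% prevalence, 100 / 0.05 = 2,000 enrolled, as stated. Neither step allows for invalid results.

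**Gap between the two estimates.** If S is accuracy on readable sera, accuracy over all sera tested with invalids counted as incorrect is S × (1 − v). The gap is S × v.

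| v | Gap at 78% sensitivity | Gap at 87% specificity |
|---|---|---|
| 2% | 1.6 points | 1.7 points |
| 5% | 3.9 points | 4.4 points |
| 10% | 7.8 points | 8.7 points |

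In whole numbers with 100 culture positives and v = 5%, the plan reports 74/95 = 77.9% (Wilson 68.6 to 85.1). Over all sera tested, the figure is 74/100 = 74.0% (64.6 to 81.6).

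**When the order of two tests changes.** Let the test with the higher conditional figure have invalid rate v and the other none. The order reverses when v exceeds 1 − (lower / higher).
- Sensitivity, 78% against 69%: 1 − 69/78 = 11.5%.
- Specificity, 90% against 87%: 1 − 87/90 = 3.3%.

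**Whether outcome 2.1 fills the gap.** Take one test run on 100 positives and 100 negatives with 10 invalid results, a reported rate of 10/200 = 5%. If all 10 are culture positives, sensitivity over all positives is 78% × 0.90 = 70.2%. If none are, it is 78.0%. The planned rate is the same in both cases. It is also unclear whether a result that was invalid first and readable on repeat counts as invalid.

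**If the all-tests per-protocol rule governs.** Should an invalid not count as an available result, one test's failure removes that serum for all 11 tests. With the same v for each test and independent failures, the expected number of positives kept out of 100 is 100 × (1 − v)^11. Putting that number into the plan's own formula gives the half-width.

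| v per test | Positives kept | Half-width (14.0 at v = 0) |
|---|---|---|
| 1% | 90 | 14.8 points |
| 2% | 80 | 15.7 points |
| 5% | 57 | 18.6 points |
| 10% | 31 | 25.0 points |

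All tests then share one denominator, so the failing test gains no separate one. It is still not penalised, and reliable tests lose precision. The removal rule's example points to test-by-test removal and the per-protocol definition to all-test removal. The plan does not reconcile them.

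**The case against.** The strongest reply is that accuracy among valid results is a legitimate estimand and fits Table 5. An invalid readout is neither a positive nor a negative, and counting it as wrong in both groups gives a worst-case bound. This stands. It is why the all-tested figure belongs beside the planned one and should not replace it.

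Failures are also not hidden. Invalid rates are reported per RDT, and the baseline section reports participants included and excluded for each test, with included samples split by reference result. That softens the point but does not settle it. Those exclusions can mix tests not run with invalid results and, under the per-protocol rule, with failures of other tests.

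The size may be small. If failures are independent between attempts, 2% to 10% still invalid after one repeat implies initial rates of about 14% to 32% (the square roots of 0.02 and 0.10). Trained laboratory staff will run the tests. If failure is a property of the serum, the repeat helps less; nothing in the documents says which applies. The sensitivity reversal at 11.5% lies outside the assumed 2% to 10% range.

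A reader might go further in three ways that the documents do not support:
- **That every invalid result is deleted.** The case report form provides a repeat, so probably only persistent invalids are lost.
- **That the plan ranks a failure-prone test first.** No ranking rule or formal comparison is specified; the risk lies in how readers use the figures.
- **That the intention-to-test set should have been used.** It is everyone enrolled, at least 2,000, while index tests are planned for the culture positives and an equal number of negatives, about 200. Some 1,800 of its members would have no index result by design.

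**Conclusion.** The point holds as a cheap improvement. The planned sensitivity and specificity are conditional on a readable result, no analysis counts device failures, and the planned invalid rates do not allow accuracy over all sera tested to be worked out.

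The size depends wholly on persistent invalid rates that the documents do not give. Over the assumed 2% to 10% range, the gap is 1.6 to 7.8 points at 78% sensitivity, and it vanishes as the rate nears 0%. A change of order in the specificity example needs only a rate above 3.3% in one test and none in the other. These differences are modest beside the planned half-width of 14 points, but they run in a known direction: the valid-only figure is never below the all-tested figure.

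The conclusion that a failing test is not penalised holds under both test-by-test and all-tests removal. Different denominators for different tests arise only under the first. The documents do not support calling the planned estimate wrong, or requiring that any ranking rest on the supplementary one.

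**What to change.** In Estimates of accuracy and the outcome paragraphs of the Statistical Analysis Plan section:

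1. State that the result after the single repeat is the one analysed.
2. Keep results from tests that were not run excluded.
3. Keep the valid-results-only estimate. Beside it, report for each test a supplementary estimate over all sera on which that test was run. Define this set explicitly: it is neither the set of all enrolled nor restricted to the all-tests per-protocol set. Count persistent invalids as not detected in culture positives and as not correctly negative in culture negatives, with Wilson intervals.
4. Report persistent invalids for each test by culture status.
5. For the five tests with separate IgG and IgM lines on the case report form, state when the overall result counts as invalid.

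No ranking need be based on the supplementary figure. The form already captures initial and repeat results, so no new data are needed. The cost is a few sentences, one extra column in the results table, the split of invalid counts by culture status, and lower supplementary figures for tests that fail.
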